**Data Collection:**

The data will be collected per the schedule outlined below:

**Table 2.** Data collection frequency.

| Procedure/Assessment       | Baseline* | Weekly | Final |
|----------------------------|-----------|--------|-------|
| Informed Consent           | X         |        |       |
| Release of Medical Records | X         |        |       |
| Screening for eligibility  | X         |        |       |
| Report of AEs              |           | X      | X     |
| Glycemic outcomes          | X         | X      | X     |
| Device Download            | X         | X      | X     |
| User Experience            |           |        | X     |

\*Includes demographics, and frequency of AEs

Investigators will assign a de-identified number to each subject and will be required to keep any study paperwork or electronic files in a secure private area. Audits will be conducted to help ensure that data is secure and entered within reasonable limits.

**Informed Consent Process:** All subjects must sign the ICF approved by the IRB to be enrolled in the study. Subjects <18 years of age will also complete the assent form. The subject will receive study team contact information (email and telephone) and be given ample opportunities to ask questions about the procedures, required schedule of data collection, and the benefits and risks of participating in the study before signing the ICF. If requested, the subject will receive a copy of the ICF to keep for their records. Subjects will be informed of any revisions to the ICF and any revisions must be signed and kept in the subject study file. Acquisition of the informed consent, and any revisions will be documented in the subject's eCRF.

**Demographics:** The following demographic data will be obtained: date of birth, gender, race, ethnicity, educational level, socioeconomic status, residence, employment status, weight, height, and type of health insurance.

**Medical History:** Medical history, including existing comorbidities deemed clinically relevant (e.g. retinopathy, nephropathy, neuropathy, history of cardiovascular events) will be collected at baseline. In addition, details specific to type 1 diabetes, including age at diagnosis, duration of disease, previous therapy, most recent HbA1c within the past 3 months, frequency of SH and DKA will be collected from the study subject in the baseline questionnaire and documented in the subject's eCRF. A new hemoglobin A1c (point-of-care or central laboratory measurement) will also be obtained at the screening visit.

**Pregnancy:** In order to reduce the risk of pregnancy, subjects of childbearing potential must agree to use an effective method of birth control while participating in this study. Acceptable methods of birth control for use in this study are barrier methods, intrauterine devices, or oral contraceptive pills. The Investigator or study staff will discuss this with the subject.

**Device Training:** All subjects will complete study device training before starting use of the study device. Subjects will be trained using the study approved device training checklist, and will be given a copy of the Study Participant Instruction Sheet. In addition to device training, the Study Participant Instruction Sheet reviews procedures for checking ketones, and when to contact study staff for assistance. Subjects will be instructed that the commercial t:connect mobile app will not connect to their study pump and is not intended to be used in the study.

Study staff will also assure subjects have set up the Dexcom G6 app with required alerts sent to study staff for the first 10 subjects.

Study staff will review with the study subject's personal contact(s) the following safety procedures, either through remote or in person training:

- 1) How to disconnect the pump
- 2) How to give glucagon
- 3) How to set up the Dexcom Follow app, and expectations for responding to alerts or phone calls from study staff.

## **4.5 Study Procedures**

### **4.5.1 Phase 1: 48-hr supervised study in-clinic/transitional environment:**

Approximately 5 subjects will be enrolled in Phase 1 of the study. The purpose of Phase 1 is to determine the safety of the Control-IQ Pro v2.0 system with use of the new features in a medically supervised, observed setting: 1) Lower target normal activity overnight and receiving auto-correction boluses, 2) Exercise Activity without autocorrections, and 3) Adjustments to meal bolusing.

After enrollment and collection of baseline data (use of the current standard Control-IQ commercial system for 1-3 weeks) subjects will be admitted in the evening and will switch from their personal t:slim X2 insulin pump with Control-IQ technology to the t:slim X2 study pump with Control-IQ Pro v2.0. Subjects will receive training on all of the new features and the instructions for using them during the ~48-hours of the study.

During this phase of the study, subjects will be remotely monitored by the study team, including a study physician, 24 hr per day. Pump and CGM alerts will be set to annunciate throughout the study. The study team will intervene if 1) CGM <70 mg/dL overnight, or 2) if a Control-IQ Low Alert occurs (indicating that the glucose is predicted to fall below 70 mg/dL within 15 minutes). Meal boluses will be supervised by study staff to ensure that the correct number of carbohydrate grams are entered into the bolus calculator.

At least one member of the study medical staff (Physician, NP) from will be present on site at all times. Up to 5 subjects will be studied at one time during the supervised phase. The goal of this

phase is to evaluate the safety of the system with correct and incorrect use of new features of the system.

**Day 1:**

Arrival: Subjects will arrive at least 3 hours prior to the dinner meal. After training of the new features of the Control-IQ Pro v2.0 are complete, subjects will switch from their personal Control-IQ pump to the Control-IQ Pro v2.0 pump. The Control-IQ Pro v2.0 pump will be configured with the lower target normal activity enabled, auto-boluses enabled for normal activity but disabled for exercise, and all sleep schedules disabled. Subjects will activate the “Eating Soon” feature ~1 hour prior to dinner, as intended for use, with a control range of 80-100 mg/dL. Subjects will then consume a dinner with at least 30 grams of carbohydrate, giving the full meal bolus prior to the meal as per their normal bolus behavior.

Subjects will use continue to use the Normal Activity setting with lower target (90-130 mg/dL) and automated correction boluses enabled for the overnight portions of the hotel study.

**Day 2:**

Subjects will consume a normal breakfast (at least 15 grams carbohydrate) with a normal meal bolus.

In the late morning of day 2, subjects will perform a ~40 minute exercise session (either on a stationary bike or treadmill, or a brisk walk outside) with the Exercise Activity setting ON (increased glucose target range, no auto boluses). Subjects will be instructed to monitor CGM values during exercise, to have fast-acting carbohydrate available and to treat themselves appropriately during the session. Study staff will be available to intervene if necessary. Subjects make take additional carbohydrate as necessary per their usual exercise preparation routine. Exercise may be discontinued for multiple low fingerstick readings, as per investigator discretion.

For lunch, subjects will perform a “late bolus” using the late bolus feature after consuming at least 30 gram carbohydrates. The late bolus should occur at least 30 minutes after completing the lunchtime meal.

For dinner, subjects will enable the “Eating Soon” feature for just over 3 hours straight prior to dinner, (re-enabling it ~every 70 minutes for 3 times total) intentionally reactivating the feature multiple times so it stays active. This intentional re-enabling of the feature is intended to assess safety if a subject were to keep this feature active for many hours in a row prior to a meal. Subjects will then bolus for their meal in the usual manner, consuming at least 30 gram carbohydrates.

Subjects will use continue to use the Normal Activity setting with lower target (90-130 mg/dL) and automated correction boluses enabled for the overnight portions of the hotel study.

**Day 3:**

Subjects will consume a normal breakfast (at least 15 grams carbohydrate) with a normal meal bolus.

In the late morning of day 3, subjects will perform a ~40 minute exercise session (either on a stationary bike or treadmill, or a brisk walk outside) with the Exercise Activity setting ON (increased glucose target range, no auto boluses). Subjects will be instructed to monitor CGM values during exercise, to have fast-acting carbohydrate available and to treat themselves appropriately during the session. Study staff will be available to intervene if necessary. Subjects make take additional carbohydrate as necessary per their usual exercise preparation routine. Exercise may be discontinued for multiple low fingerstick readings, as per investigator discretion.

For lunch, subjects will consume at least 30 gram carbohydrates, but will skip their meal bolus (missed meal bolus scenario) with the goal of letting the system bring down their blood sugar after the meal.

[figure not shown]
Subject will be asked to set-up/re-enable sleep schedules after lunch if they desire, or may continue to use the normal activity setting overnight with the required targets per each week of the study.

Subjects will be discharged home to begin Phase 2, as long as their CGM values are approaching 80-180 mg/dL at least 90 minutes after lunch, and remaining steady per investigator discretion.

Additional meals and snacks may be consumed by subjects as needed for satiety or treatment of hypoglycemia.

A schematic of the supervised challenges is shown below in Figure 1. The investigator on site may opt to give additional insulin boluses or carbohydrate treatments as necessary or end particular use of a feature, at their discretion for subject safety:

450 **Figure 1.** Schedule of supervised challenges.

451  
452 During Phase 1, the following hyper and hypoglycemic treatment plan will be used:

453 **Table 3.** Hypoglycemia and Hyperglycemia Prevention and Treatment Plan during the  
454 supervised, 48 hour session.

| Condition  | Action Taken   |
|--|--|
| CGM reading <70 mg/dL                                      | 
A confirmatory fingerstick measurement will be performed.
 
If fingerstick glucose <math>\geq 70</math> mg/dL, treatment may be initiated by the investigator (~4-16 g fast acting carbohydrate) per investigator discretion. Subjects will then perform a follow-up fingerstick measurement 15 minutes after treatment if CGM < 70 mg/dL.
 
If fingerstick glucose < 70 mg/dL, treatment will be initiated by the investigator (~4-16 g fast acting carbohydrate) per investigator discretion. Subjects will then perform a follow-up fingerstick measurement 15 minutes after treatment if CGM < 70 mg/dL.
 
This protocol will be repeated until the fingerstick is >70 mg/dL per standard clinical treatment for hypoglycemia.
 |
| Any time a subject has subjective symptoms of hypoglycemia | A fingerstick blood glucose measurement will be performed. Fast-acting carbohydrates may be given to any subject who is symptomatic or requests treatment.   |

|   |   |
|---|---|
| CGM reading is >300 mg/dL for more than 1 hour  | 
A confirmatory fingerstick measurement will be performed.
 
If the subject's BG is confirmed to be >300 mg/dL, then ketones will be checked using the study-approved ketone meter.
   |
| BG confirmed >300 mg/dL for more than 1 hour and ketones are <0.6 mmol/L                      | 
A manual correction bolus may be delivered via the pump. Fingerstick BG and ketone measurements will be repeated after 1 hour. The correction dose given may be adjusted by the investigator.
 
If BG fails to decrease by a minimum of 50 mg/dL in 1 hour, then study staff will replace the subject's infusion set with a new infusion set and the correction bolus will be repeated per the investigator's discretion.
   |
| BG confirmed >300 mg/dL for more than 1 hour and ketones are $\geq$ 0.6 mmol/L                | 
A manual correction bolus may be delivered via injection to assure proper absorption in the setting of likely infusion set failure. Fingerstick BG and ketone measurements will be repeated after 1 hour. The correction dose given may be adjusted by the investigator.
 
The study staff will replace the subject's infusion set with a new infusion set and the correction bolus will be repeated per the investigator's discretion. Control-IQ will be disabled by the investigator for the next 2-4 hours and until BG has returned to < 180 mg/dL.
 |
| Subject loses consciousness or has a seizure, or subject is unable to take oral carbohydrates | 
1 mg of IM glucagon or 3 mg nasal glucagon will be administered and 911 will be called. The study will be stopped immediately until sponsor conducts a full investigation to determine the root cause for the compromised system performance and is able to address all issues. Sponsor will also communicate the results of this root cause investigation to FDA and to study investigators.
  |
| No heart rate, no blood pressure  | 
Perform resuscitation, call 911, and transfer subject to ER.
 
Sponsor will conduct a full investigation to determine the root cause for the compromised system performance. Sponsor will also communicate the results of this root cause investigation to FDA and to study investigators.
  |

To allow subjects to continue using the study pump at discharge and proceed with further use of the study device in additional subjects, the study pump must be downloaded by study staff and the device download reviewed by the study PI and Tandem staff. The following success criteria must be met for continuation into the outpatient phase of the study:

- 1) No serious adverse events related to the study device or procedures.
- 2) No unanticipated adverse device effects.
- 3) Subject will be reminded to schedule a sleep activity setting if preferred for home use.
- 4) Subject must be able to complete system-related use tasks independently to be eligible to continue in the study as per the device training checklist.
- 5) Subjects must show understanding of the outpatient study safety plan, as described below in Phase 2: At-home study, as well as in sections 7.9 and 7.10, to include continued real-time sharing of glycemic data with the Dexcom G6 app and responding to calls from the study team that may result from sharing alerts.

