### 2.3 Study Endpoints

#### 1) Primary Safety Endpoints:

- a. Significant Hypoglycemia time <54 mg/dL
- b. Severe hypoglycemia (needing assistance)
- c. DKA
- d. Serious Adverse Events

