#### **4.5.2 Phase 2: At-home study**

After enrollment and collection of baseline data, subjects will switch from their personal t:slim X2 insulin pump with Control-IQ technology to the t:slim X2 study pump with Control-IQ Pro v2.0. Subjects will receive training on all of the new features and the instructions for using them during the following week of the study. Subjects will keep a log of their use of the required features of the new pump for the week. Subjects will be required to attend the study site visit each week (+/- 3 days), during which time their pump and CGM data will be downloaded and they will receive instructions for the following week.

Remote real-time monitoring using the Dexcom G6 app will be required to be shared by subjects with their local contact(s) throughout the study, and with study staff for the first 10 subjects. After the first 10 subjects complete the study, required real-time alerts to study providers may be removed for future subjects after sponsor review and approval. This review will certify that:

- 1) No severe hypoglycemia events related to algorithm delivered automated insulin dosing occur that required study staff intervention because the subject was not aware/treating appropriately in the first 10 subjects.
- 2) No severe hyperglycemic events related to algorithm delivered automated insulin dosing occurred that required study staff intervention because the subject was not aware/treating appropriately in the first 10 subjects.

During the weekly required visit, the Control-IQ software in their pump will be reconfigured to support the following week's features. The configuration tool will be run by clinical staff from an approved study laptop, using Bluetooth to reconfigure the pump. If a software update to the pump is not required at the weekly visit, and the subject is able to download their pump remotely, the visit may be performed remotely per investigator discretion.

After each weekly download, staff will review the download to document correct use of each feature, and document this on the study CRF. If a subject is using a feature not per the study instructions (for example, using eating soon not just prior to meals), subjects will be re-educated

on the relevant instructions and this will be documented in the study CRF. All subjects will receive a phone call 48 hours (+/- 1 day) after each weekly feature update to review any new questions that may arise.

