### **6.5 Risk of Hypoglycemia**

As with any person having T1D and using insulin, there is always a risk of having a low blood sugar (hypoglycemia). The frequency of hypoglycemia should be no more and possibly less than it would be as part of daily living. Symptoms of hypoglycemia can include sweating, jitteriness, and not feeling well. Just as at home, there is the possibility of fainting or seizures (convulsions) and that for a few days the participant may not be as aware of symptoms of hypoglycemia. A CGM functioning poorly and significantly over-reading glucose values could lead to inappropriate insulin delivery.

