## 8. Adverse Events, Device Issues, and Stopping Rules

### 8.1 Adverse Events

Adverse Event (AE): Any untoward medical occurrence in a study participant, irrespective of the relationship between the adverse event and the device(s) under investigation (see section 8.2 for reportable adverse events for this protocol).

Serious Adverse Event (SAE): Any untoward medical occurrence that:

Results in death.

Is life-threatening; (a non-life-threatening event which, had it been more severe, might have become life-threatening, is not necessarily considered a serious adverse event).

Requires inpatient hospitalization or prolongation of existing hospitalization.

Results in persistent or significant disability/incapacity or substantial disruption of the ability to conduct normal life functions (sight threatening).

Is a congenital anomaly or birth defect.

Is considered a significant medical event by the investigator based on medical judgment (e.g., may jeopardize the participant or may require medical/surgical intervention to prevent one of the outcomes listed above).

Unanticipated Adverse Device Effect (UADE): Any serious adverse effect on health or safety or any life-threatening problem or death caused by, or associated with, a device, if that effect, problem, or death was not previously identified in nature, severity, or degree of incidence in the investigational plan or application (including a supplementary plan or application), or any other unanticipated serious problem associated with a device that relates to the rights, safety, or welfare of participants (21 CFR 812.3(s)).

Adverse Device Effect (ADE): Any untoward medical occurrence in a study participant which the device may have caused or to which the device may have contributed (Note that an Adverse Event Form is to be completed in addition to a Device Deficiency or Issue Form).

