## 8.2 Reportable Adverse Events

For this protocol, a reportable adverse event includes any untoward medical occurrence that meets one of the following criteria:

1. A serious adverse event
2. An Adverse Device Effect as defined in section, unless excluded from reporting in section 8.9
3. An Adverse Event occurring in association with a study procedure
4. Hypoglycemia meeting the definition of severe hypoglycemia as defined below
5. Diabetic ketoacidosis (DKA) as defined below or in the absence of DKA, a hyperglycemic or ketosis event meeting the criteria defined below

Hypoglycemia and hyperglycemia not meeting the criteria below will not be recorded as adverse events unless associated with an Adverse Device Effect. Skin reactions from sensor placement are only reportable if severe and/or required treatment.

Pregnancy occurring during the study will be recorded.

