## 8.3 Hypoglycemic Events

Hypoglycemia not associated with an Adverse Device Effect is only reportable as an adverse event when the following definition for severe hypoglycemia is met: the event required assistance of another person due to altered consciousness, and required another person to actively administer carbohydrate, glucagon, or other resuscitative actions. This means that the participant was impaired cognitively to the point that he/she was unable to treat himself/herself, was unable to verbalize his/ her needs, was incoherent, disoriented, and/or combative, or experienced seizure or coma. These episodes may be associated with sufficient neuroglycopenia to induce seizure or coma. If plasma glucose measurements are not available during such an event, neurological recovery attributable to the restoration of plasma glucose to normal is considered sufficient evidence that the event was induced by a low plasma glucose concentration.

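### The Phase 1 gate to home use has no severe-hypoglycemia criterion, so one orally treated severe low need not hold back the other and additional subjects

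*Combined protocol and SAP*

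**What the plan says.** Section 4.5.1 (the success criteria after Table 3) governs two decisions: whether a subject leaves Phase 1 on the study pump, and whether the device is then used in further subjects. Before either, the pump must be downloaded and the download reviewed by the study investigator and sponsor staff. Five criteria follow. The first is "No serious adverse events related to the study device or procedures" and the second is the absence of unanticipated adverse device effects (UADEs). The other three cover sleep settings, independent use of the system, and understanding of the home safety plan.

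Table 3 stops the study, pending a sponsor root-cause investigation, when this row is met: "Subject loses consciousness or has a seizure, or subject is unable to take oral carbohydrates".

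Section 8.3 defines severe hypoglycemia more widely. The subject needed help because of altered consciousness, "and required another person to actively administer carbohydrate, glucagon, or other resuscitative actions". Incoherence, disorientation or combativeness is enough; seizure or coma is not required.

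Section 8.12 item 4 ends study-device use for a subject after one such episode (or one DKA) in Phase 1. Section 8.13 suspends device use after a single severe event if a system malfunction caused it. Otherwise it requires a stop at 3 or more severe hypoglycemia episodes, whatever the cause.

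**The concern.** Phase 1 exists to establish safety under supervision before the device is used at home, and it deliberately includes incorrect use of the new features. Severe hypoglycemia is one of the four primary safety endpoints in section 2.3. One would expect the rule that opens home use to refer to that endpoint. Instead it refers to two regulatory labels, related SAE and UADE, and a severe low need not receive either.

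At stake is a go/no-go decision. After a severe low in a group of about 5 supervised subjects, the protocol read literally could let everyone except the affected subject proceed, without requiring anyone to decide explicitly that this was acceptable.

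**Working it through.** No calculation in the plan lies behind this gate, so the check is a trace of the rules. Take one Phase 1 subject who becomes disoriented from a low glucose. Staff must actively give oral carbohydrate, the subject swallows it and recovers, and no malfunction is found.

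1. **Section 8.3.** Met. Consciousness is altered and another person gives carbohydrate, so this is severe hypoglycemia and counts toward the primary endpoint.
2. **Table 3, study halt.** Not met. There is no loss of consciousness, no seizure, and the subject can take oral carbohydrate. The row that applies is the one for a low CGM reading, whose action is to treat and recheck.
3. **Section 4.5.1, criterion 1.** Failed only if the event is a related SAE. Section 8.2 lists "Hypoglycemia meeting the definition of severe hypoglycemia as defined below" as a reportable item in addition to SAEs, and section 2.3 lists the two as separate endpoints, so the label is not automatic. If there is no death, threat to life, hospitalization or lasting disability, the remaining route in section 8.1 is that the event "Is considered a significant medical event by the investigator based on medical judgment".
4. **Section 4.5.1, criterion 2.** Failed only if the event is a UADE. Hypoglycemia is an identified risk (section 6.5: "there is always a risk of having a low blood sugar"), so this label is doubtful. It is not excluded, because the definition also turns on severity and degree of incidence.
5. **Section 8.12 item 4.** Triggered. This subject stops using the device and does not take it home.
6. **Section 8.13, malfunction route.** Not triggered in this scenario.
7. **Section 8.13, count route.** Not triggered: 1 episode is below 3.

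The affected subject is therefore stopped, and no written criterion stops anyone else. With about 5 Phase 1 subjects and about 25 additional ones, those free to proceed number (5 − 1) + 25 = 29.

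The count rule leaves room for a second event. Because 8.12 item 4 removes a subject after one Phase 1 episode, two episodes would come from two different subjects: 2/5 = 40% of Phase 1, still below the stop at 3. Then (5 − 2) + 25 = 28 could proceed. These are limits set by the rules; they do not estimate how likely the events are.

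For comparison, section 4.5.2 sets a later gate, for dropping real-time alerts to study staff after the first 10 subjects. It does name the event: "No severe hypoglycemia events related to algorithm delivered automated insulin dosing occur that required study staff intervention", qualified by the subject being unaware or not treating appropriately.

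**The case against.** A reader might infer that a subject with a severe low in Phase 1 could go home on the study pump. The documents do not support that: 8.12 item 4 ends device use for that subject whatever label the event receives.

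A reader might also infer that nothing stands between such an event and wider use. That is too strong. Section 4.5.1 makes the download review by the investigator and the sponsor a precondition in every case, and 8.13 lets the sponsor suspend the study on the totality of safety data. What the review lacks is a criterion. It is a review of device data, and nothing tells the reviewers that a severe low means waiting. A reportable event that is neither an SAE nor a UADE has no fixed reporting deadline (section 8.11). The sponsor reviews each adverse event form (section 8.4), but that review is not tied to the gate.

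The best counter-argument is that the labels would usually catch the event. The judgment clause in 8.1 gives as examples events that may jeopardize the participant or need intervention to prevent a listed outcome, and a disoriented subject rescued by staff fits that closely. The items in 8.2 can overlap, so listing them separately does not show that a severe low is not serious. Malfunction is defined in 8.1 to include failure to perform as intended, which could cover harmful over-delivery by the algorithm. All of this stands and narrows the gap. It still leaves the decision to a judgment, and section 8.14 provides only for site investigator review.

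The scenario is also improbable. Subjects with severe hypoglycemia in the past 6 months are excluded, monitoring runs 24 hours a day with medical staff on site, and staff act on a CGM value below 70 mg/dL overnight or on a predictive low alert. The comparison with the gate in 4.5.2 is only suggestive, because that gate concerns staff alerts and covers only algorithm-related events that needed staff intervention.

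**Conclusion.** The point holds in a limited form. The gate in 4.5.1 decides for the other Phase 1 subjects and for additional subjects as well as for the subject at hand, yet it has no severe-hypoglycemia criterion. One episode under 8.3 treated with oral carbohydrate removes one subject. Unless it is labelled a related SAE or a UADE, or results from a malfunction, no stated criterion holds back the remaining 29 or so planned device users.

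This assumes that the investigator does not call the event a related SAE and that no malfunction is found. It also uses the approximate group sizes of 5 and 25. The documents give no basis for a probability, and under this level of supervision the event should be rare. No separate gap for DKA has been shown. This is an inexpensive improvement to a go/no-go rule and does not amount to a flaw in the design.

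**What to change.** Add one criterion to the list in section 4.5.1, for example: *No severe hypoglycemia (section 8.3) in any Phase 1 subject. If one occurs, discharge of other subjects on the study pump and use in additional subjects wait until the sponsor has reviewed the cause and documented the decision to proceed.* DKA under section 8.4 may be added so that the gate matches 8.12 item 4.

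Beyond the existing download review, this adds an explicit trigger, a review of cause and a record of the decision. It requires a protocol amendment with IRB approval before use (section 10.5) and, if an event occurs, a pause in progression. Sample size, visits and data collection do not change.
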